12.2 Populations for Analyses

Safety

All analyses of safety will be made on the safety population which will be defined as all subjects who are randomized and received treatment at least once during the study. The safety population will be analyzed as per treatment received.

Efficacy

Efficacy analyses will be based on the Modified Intention-To-Treat (MITT) population which is defined as all randomized subjects with at least one post baseline assessment of efficacy. This will be the primary population for the efficacy analysis which will be performed as per the planned randomized treatment.

The Per-Protocol (PP) population will be a subset of the MITT population. Subjects with a protocol violation that is deemed to affect efficacy assessments in all study periods will be excluded from the PP population. Subjects with a protocol violation that is deemed to affect efficacy assessments in some (but not all) study periods will be part of the PP population, but their data will be excluded from the period(s) affected by the protocol violation for a PP analysis. An analysis on the PP population will be performed for the primary efficacy variable if the number of subjects evaluable in any of the treatment groups for the MITT and PP

populations differs by 10% or more. The decision on whether a PP analysis will be performed will be made prior to study unblinding.

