1.2 Study Objectives

Objectives	Endpoints
Primary	
To compare the maximum incisal bite force until maxillary denture dislodgement of two experimental denture adhesives to no adhesive over 12 hours	Area over baseline in bite force over 12 hours
Secondary	
To compare the maximum incisal bite force until maxillary denture dislodgement of two experimental denture adhesives to no adhesive for time periods up to 9 hours.	Area over baseline up to 0.5, 1, 3, 6 and 9 hours
Safety	
To assess the local tolerability of two experimental denture adhesives	Treatment emergent adverse events and incidents

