4.1.3 Analysis Populations

3 analysis populations are defined.

Population	Definition / Criteria	Analyses Evaluated
Safety	
• All randomized subjects who receive treatment at least once during the study.• This population will be based on the treatment the subject actually received.	
• Study Population• Safety
Intent-To-Treat (Modified) (MITT)	
• All randomized subjects with at least one post baseline assessment of efficacy.• This population will be based on the treatment to which the subject was randomized.• Any subject who receives a treatment randomization number will be considered to have been randomized.	
• Efficacy
Per-Protocol (PP)	
• Subset of the MITT population.• Subjects with a protocol violation that is deemed to affect efficacy assessments in all study periods will be excluded from the PP population.• Subjects with a protocol violation that is deemed to affect efficacy assessments in	
• Efficacy

Population	Definition / Criteria	Analyses Evaluated
	
some (but not all) study periods will be part of the PP population, but their data will be excluded from the period(s) affected by the protocol violation for a PP analysis.
 
• Performed for the primary efficacy variable if the number of subjects evaluable in any of the treatment groups for the MITT and PP populations differs by 10% or more. The decision on whether a PP analysis will be performed will be made prior to study unblinding.	

The numbers of subjects included in each of the analysis populations, and the number excluded from each population broken down by the reason for exclusion will be presented in Table 3.

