4.4.1 Adverse Events and Serious Adverse Events

Adverse events (AEs) will be categorized as oral or non-oral by the examiner prior to database lock. AEs will be deemed to be treatment emergent if they occur after the first supervised use of the randomized treatment. No specific risks or anticipated adverse device effects are expected to be observed within this study, however all AEs and medical device incidents will be assessed to evaluate the tolerability and safety of the treatments. No formal statistical analyses of AEs will be performed. AEs will be listed in Listing 2. Serious Adverse Events (SAEs) will be listed in Listing 3.

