4.4.2 Medical device events

The medical devices in this study are the supplied denture adhesive creams, the denture cleansing paste and the denture cleaning brushes. Medical device incidents involving an AE will be included in the AE listing. No formal statistical analyses of medical device events will be performed.

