	AOB ₀₋₃							

	AOB ₀₋₆							
	AOB ₀₋₉							
	AOB ₀₋₁₂							
Experimental Denture Adhesive 2	AOB _{0-0.5}							
	AOB ₀₋₁							
	AOB ₀₋₃							
	AOB ₀₋₆							
	AOB ₀₋₉							
	AOB ₀₋₁₂							
Super Poligrip Free Adhesive Cream	AOB _{0-0.5}							
	AOB ₀₋₁							
	AOB ₀₋₃							
	AOB ₀₋₆							
	AOB ₀₋₉							
	AOB ₀₋₁₂							
No Adhesive	AOB _{0-0.5}							
	AOB ₀₋₁							
	AOB ₀₋₃							
	AOB ₀₋₆							
	AOB ₀₋₉							
	AOB ₀₋₁₂							

Table 14. AE, TEAE, Product-related AE, Medical device related AE, SAE, Medical device event

	Total
AE; N (%)	
Oral AE; N (%)	
TEAE; N (%)	
Product-related AE; N (%)	
Medical Device related AE; N (%)	
SAE; N (%)	
Medical Device Event; N (%)	

Listing 1. Protocol deviations

ID	Deviation date	Visit(s) affected	Nature of deviation	Missed applications	Additional applications	Other	Description	Comments	Exclusion from PP

Listing 2. Adverse events.

ID	Age	Sex	Race	AE	Start date	Stop date	COVI D-related	Serious	Product-related	Oral	TEAE	Product Action	Outcome	SAE	Ongoing	Expected	Frequency	Discontinue	Comment

Listing 3. Medical device events.

ID	Device type	Incident type	Incident type other	Start date	Stop date	Outcome	Treatment given	Corrective action	AE	Device cause AE	Subject Withdrawn	Device available	Device details

Listing 4. Serious adverse events.

{same as Listing 2, subset to SAEs}

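### No planned adverse-event output identifies the treatment received, so the outputs as written cannot show the tolerability of either experimental adhesive

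*SAP*

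**What the plan says.** The safety objective concerns specific products: "To assess the local tolerability of two experimental denture adhesives" (SAP 1.2, with the same objective in Protocol 3). Protocol 12.2 states that "The safety population will be analyzed as per treatment received". SAP 4.1.3 says of the Safety population that "This population will be based on the treatment the subject actually received", and SAP 4.4 draws all safety results from that population.

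For AEs, SAP 4.4.1 rules out formal testing and then says "AEs will be listed in Listing 2". It requests no table. The summary appears only in the list of tables and in the shell headed "Table 14. AE, TEAE, Product-related AE, Medical device related AE, SAE, Medical device event". The Listing 4 shell, for serious events, is "same as Listing 2, subset to SAEs". The one timing rule, in Protocol 12.3.3 and SAP 4.4.1, calls an AE treatment emergent if its onset follows the first supervised application of the assigned treatment.

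SAP 4.4.3 and 4.4.4 keep the oral soft tissue (OST) and oral hard tissue (OHT) examinations out of all tables and listings. Treatment-emergent abnormalities go to the AE listing.

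**The concern.** In a four-period crossover every completer receives all four treatments. A count of subjects with an event therefore says nothing about a given product unless each event is tied to a period. A pooled column would show an oral lesion after an experimental adhesive and one in a no-adhesive period in the same way.

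At stake is the study's only safety objective. If events are tied to products only after the results are known, there is discretion over which product carries each one. Nothing in the primary or secondary efficacy analysis depends on this.

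**Working it through.** The plan states no figure on this point, so the check is a comparison of text, list of tables and shells.

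**1. Columns in the AE outputs (SAP shells).**
- Table 14: seven rows (AE, oral AE, treatment-emergent AE, product-related AE, device-related AE, SAE, device event) and one data column, Total. Treatment columns: 0 of 4.
- Listing 2: 20 columns (ID, age, sex, race, AE, start date, stop date, COVID-related, serious, product-related, oral, TEAE, product action, outcome, SAE, ongoing, expected, frequency, discontinue, comment). Columns for treatment, period or visit: 0 of 20. The product-related column does not name the product.
- Listing 4: same columns, so again 0 of 20.

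Outputs that identify treatment: 0 of 3.

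**2. Is this only a shell problem?** The shells are marked as a rough draft, and they depart from the text elsewhere: the MITT Table 4 shell has treatment columns although SAP 4.2 says overall only. A shell alone would not settle the matter. Here three sources agree:
- SAP 4.4.1 asks for listings and no display by treatment.
- The Table 14 entry in the list of tables has no treatment split, whereas the entries for Tables 7, 10, 12 and 13 do.
- The shell has only Total.

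The Table 3 shell gives the Safety row four treatment columns plus Total, so the denominators are already planned. Listing 1 has a column for visits affected by a deviation; the AE listing has no counterpart. SAP section 5 declares no change to the safety analysis.

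**3. Does another output fill the gap?** Examination findings reach the reader only as AEs: in Listing 2, and pooled in Table 14. The shell "Listing 3. Medical device events" may identify the product for a device incident, but it does not cover AEs in general. SAP 4.4.2 sends the overlap back to the same place: "Medical device incidents involving an AE will be included in the AE listing".

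**4. Does any rule assign an event to a treatment?** The treatment-emergent rule separates time before first use from time after it, not one treatment from another. It leaves open:
- events between consent and first use, which are collected (Protocol 10.3) although screening may be up to 28 days earlier (Protocol 8.1);
- events between periods, with washouts of 1 to 28 days (Protocol 8.2.1).

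Events in the 5 days after the last administration or procedure (Protocol 10.3) follow only the last treatment and are easily assigned once a rule exists.

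**5. Illustration (assumed count; the documents give no AE rate).** Suppose 6 of 45 treated subjects have an oral treatment-emergent AE. Table 14 shows 6/45 = 13.3%. If all 45 received every treatment, that entry fits 6/45 = 13.3% on one experimental adhesive and 0/45 on the other three treatments. It fits equally well 2/45 = 4.4% on each of two treatments and 1/45 = 2.2% on each of the other two.

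**The case against.** The best defence is that SAP 4.4 takes all safety results from a population defined by actual treatment, so the by-treatment intent is already stated and only an unfinished shell is at fault. On a narrower reading, that wording only says that actual treatment replaces randomized treatment where they differ. A Total column would then not contradict Protocol 12.2. The narrower reading is tenable, so the claim that Table 14 breaches the protocol outright, which a reader might infer, is not secure. The point survives either way. On the first reading no output carries out the stated intent; on the second the product-specific objective still goes unanswered.

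It can also be said that safety is descriptive, that each treatment is a single supervised application, that OST examinations before and after each treatment day bracket same-day findings (Protocol 9.3.1), and that the investigator assesses causality for every AE (Protocol 10.5.2). All of this stands and limits the weight of the point. It does not put the treatment into any AE output.

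A by-treatment table also has limits of its own. SPF may be used on the mandibular denture on any test day, including no-adhesive days (Protocol 8.1.6, SAP 1.3), and habitual users may continue their own adhesive between visits (Protocol 5.5.3). A no-adhesive column would not be adhesive-free for these subjects.

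**Conclusion.** The point holds as a gap in the planned outputs and in the attribution rule. None of the three AE outputs identifies treatment, and no rule links an event to one of the four treatments. Followed as written, the plan gives pooled counts that cannot show the tolerability of either experimental adhesive. It should be corrected, but it does not touch efficacy or study success.

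Two stronger readings are not supported. A reader might infer that the safety information is lost; it is not, because AE start dates and treatment by period are recorded and treatment at onset can largely be derived. A reader might also infer from the long washouts that many events would be ambiguous. The documents give no AE rate, and counting days outside treatment days would not estimate this, since some of those days are follow-up after the last treatment only.

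The conclusion assumes that the final outputs follow SAP 4.4.1, the list of tables and the shells.

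**What to change.** 1. Give Table 14 four treatment-received columns plus Total, as in the Table 3 shell. Use as denominators the Safety-population subjects exposed to each treatment. Show events between consent and first use in a separate pre-treatment category.
2. Add treatment received and period at onset to Listings 2 and 4.
3. Before unblinding, state one attribution rule in SAP 4.4.1, for example the most recent treatment received before onset. Flag between-period events and subjects with SPF on the mandibular denture.
4. In the same edit, cite Table 14 in SAP 4.4.1 and reconcile the listing numbers: that section puts SAEs in Listing 3, while the shells use Listing 3 for device events and Listing 4 for SAEs.

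The cost is SAP text and shells only, using data already collected. The downside is that attribution of between-period events stays imperfect under any rule, and the no-adhesive column needs a footnote on mandibular SPF and on subjects' own adhesive between visits.

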4.4.4 Oral Hard Tissue Examination

Oral hard tissue exam (OHTE) will be collected in the study database but will not be reported in tables or listings. Any treatment emergent abnormal findings will be included in the AE listing. No formal statistical analyses of OHTE will be performed.

5 Changes to the Protocol Defined Statistical Analysis Plan

The repeated measures analysis of covariance described in section 4.3.2 to generate the bite force adjusted means and standard errors at each time point was added to create the figure requested by GSK.

List of Tables, Figures, and Listings

Tables

1. Premature discontinuation
2. Reason for Discontinuation (for subjects with premature discontinuation)
3. Analysis populations
4. Demographic characteristics
5. Baseline characteristics
6. ANOVA table for AOB₀₋₁₂
7. Adjusted means, standard errors, and 95% confidence intervals for AOB₀₋₁₂ by treatment.
8. Adjusted differences, standard errors, and 95% confidence intervals for AOB₀₋₁₂ between pairs of treatments.
9. ANOVA tables for AOB_{0-0.5}, AOB₀₋₁, AOB₀₋₃, AOB₀₋₆, and AOB₀₋₉
10. Adjusted means, standard errors, and 95% confidence intervals for AOB_{0-0.5}, AOB₀₋₁, AOB₀₋₃, AOB₀₋₆, and AOB₀₋₉ by treatment.
11. Adjusted differences, standard errors, and 95% confidence intervals for AOB_{0-0.5}, AOB₀₋₁, AOB₀₋₃, AOB₀₋₆, and AOB₀₋₉ between pairs of treatments.
12. Bite force adjusted means and standard errors over time by treatment.
13. Bite force, AUC, and AOB summary statistics by treatment and time
14. Number and percent of subjects with AE, Oral AE, TEAE, Product-related AE, Device Incidents, SAE

{note, tables 4-13 will be repeated as 4b-13b if the PP analysis is performed}

Listings

1. Protocol deviations.
2. Adverse events.
3. Medical device events.
4. Serious adverse events.

Figures

1. Line plot of bite force adjusted means over time with SE error bars by treatment.
2. Subject-level profile plots (connected scatter plots) of AOB_{0-0.5}, AOB₀₋₁, AOB₀₋₃, AOB₀₋₆, AOB₀₋₉, and AOB₀₋₁₂, with all treatments overlayed on the same figure. Plotted by subject.
3. Plot of adjusted differences with 95% confidence intervals for AOB₀₋₁₂ between pairs of treatments.

Rough draft of table shells

Table 1. Premature discontinuation

	N (%)
No	
Yes	
Total	

Table 2. Reason for Discontinuation (for subjects who did not complete study), check all that apply

	N
Subject Discontinued/Withdrew from the study due to COVID-19 pandemic	

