Subject withdrew from the study at his or her own request	
Subject did not meet study criteria; specify the criterion or assessment not met	
Adverse event(s)	
The discretion of the investigator or sponsor for safety,	
Behavioral reasons	
Inability of the subject to comply with the protocol required schedule of study visits or procedures.	
Protocol violation that may impact the subject's safety	
Withdrawal of informed consent	
Subject lost to follow-up	
Pregnancy	
Death	

Table 3. Analysis populations

	Total	Experimental Denture Adhesive 1	Experimental Denture Adhesive 2	Super Poligrip Free Adhesive Cream	No Adhesive
	N	N	N	N	N
Safety					
MITT					
Reason for MITT exclusion					
PP					
Reason for PP exclusion					

Table 4. Demographic characteristics. MITT population.

	Total	Experiment al Denture Adhesive 1	Experiment al Denture Adhesive 2	Super Poligrip Free Adhesive Cream	No Adhesive
Age; N, Mean (SD), Median, Minimum-Maximum					
Sex					
Male; N (%)					
Female; N (%)					
Race (check all that apply)					
American Indian or Alaska Native; N (%)					
Asian; N (%)					
Black or African American; N (%)					
Native Hawaiian or Other Pacific Islander; N (%)					
White; N (%)					
Other; N (%)					
Ethnicity					
Hispanic or Latino; N (%)					
Not Hispanic or Latino; N (%)					

Table 4b. Demographic characteristics. PP population.

	Total	Experiment al Denture Adhesive 1	Experiment al Denture Adhesive 2	Super Poligrip Free Adhesive Cream	No Adhesive
Age; N, Mean (SD), Median, Minimum-Maximum					
Sex					
Male; N (%)					
Female; N (%)					
Race (check all that apply)					
American Indian or Alaska Native; N (%)					
Asian; N (%)					
Black or African American; N (%)					
Native Hawaiian or Other Pacific Islander; N (%)					
White; N (%)					
Other; N (%)					
Ethnicity					
Hispanic or Latino; N (%)					
Not Hispanic or Latino; N (%)					

Table 5. Baseline characteristics. MITT population.

	Total	Experiment al Denture Adhesive 1	Experiment al Denture Adhesive 2	Super Poligrip Free Adhesive Cream	No Adhesive
	N (%)	N (%)	N (%)	N (%)	N (%)
Denture bearing tissue evaluation					
Ridge shape					
Flat					
V-shaped					
U-shaped					
Tissue Resiliency					
Flabby					
Resilient					
Firm					
Border Tissue Attachment					
Low					
Medium					
High					
Well-made Assessment					
Has this denture clinically acceptable vertical dimension, freeway space, horizontal occlusal relationships and border extensions?					
Acceptable					
Unacceptable					

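### The planned adverse-event outputs pool all four crossover treatments, although the only safety objective concerns the two experimental adhesives

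*SAP*

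**What the plan says.** The safety objective, in Protocol section 3 and SAP 1.2, is "To assess the local tolerability of two experimental denture adhesives". Its endpoint is treatment-emergent adverse events and incidents.

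Protocol 12.2 states: "The safety population will be analyzed as per treatment received". SAP 4.1.3 says of the safety population: "This population will be based on the treatment the subject actually received".

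SAP 4.4.1 rules out formal testing of adverse events, sends them to a listing, and defines treatment emergence: "AEs will be deemed to be treatment emergent if they occur after the first supervised use of the randomized treatment". It does not mention display by treatment. SAP 4.4.3 and 4.4.4 keep the soft- and hard-tissue examination results out of all tables and listings. Treatment-emergent abnormal findings go into the adverse-event listing.

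The one adverse-event summary appears in the draft shells at the end of the SAP as "Table 14. AE, TEAE, Product-related AE, Medical device related AE, SAE, Medical device event", with one column, Total. Listing 2 holds the adverse events, and Listing 4 is the same layout restricted to serious events.

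**The concern.** The objective asks about two particular products. In a four-treatment, four-period crossover, a subject who completes the study has received both of them, the positive control and no adhesive. A count of subjects with an event at any time in the study therefore mixes four conditions. If the listing also omits the treatment, a reader cannot separate them.

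At stake is whether the report, produced as planned, can answer its own safety question. If a few subjects had oral irritation, the sponsor would want to know whether the events clustered on one experimental adhesive, were shared with the marketed product, or arose equally with no adhesive. The no-adhesive and positive-control periods would give useful context for tolerability, but only if events are shown against them.

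**Working it through.** No arithmetic is needed. The check looks for any route in the planned outputs from an event to a treatment.

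1. **Table 14 shell.** It has seven rows: AE, oral AE, TEAE, product-related AE, device-related AE, SAE and device event. It has one column, Total. Treatment columns: 0 of 4.

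2. **Listing 2 shell.** Its 20 columns are ID, age, sex, race, AE, start date, stop date, COVID-related, serious, product-related, oral, TEAE, product action, outcome, SAE, ongoing, expected, frequency, discontinue and comment. Fields for treatment, period, visit or sequence: 0 of 20. The product-related and product-action fields name no product. Listing 4 inherits the same columns.

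3. **Start date as an indirect route.** A date identifies a treatment only if the reader also has each subject's application dates and sequence. No planned table or listing shows either. Visits are 1 to 28 days apart (Protocol 8.2.1), so the dates differ between subjects.

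4. **Other outputs.** Listing 1 has a field for visits affected, but it covers protocol deviations. Listing 3 has device type and device details, but it covers device events. Free text in the Listing 2 comment column might name a product, but it is not a defined field. The tissue examinations offer no second route, because their results are not tabulated or listed.

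5. **Treatment-emergence rule.** Read naturally, it separates events before the first study treatment from everything after. An event after Visit 2 is treatment emergent whichever treatment preceded it. Protocol 10.3 collects events from consent until 5 days after the last administration or procedure, so events can begin between visits. Neither document says which treatment such an event belongs to.

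6. **Is the single column an artefact of reading the PDF?** That is unlikely. The shells of Tables 3, 4 and 5 show Total plus four treatment columns. The "Table 3. Analysis populations" shell includes the safety population, so the number of subjects treated with each product is already planned. The denominators exist without the matching event counts.

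The result is that no defined field in any planned output links an adverse event to a treatment.

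**The case against.** The strongest reply is that the shells are headed as a rough draft and do not always follow the SAP text. SAP 4.2 says demographics for the modified intention-to-treat population are tabulated overall only, yet the Table 4 and Table 5 shells for that population have treatment columns. SAP 4.2.2 lists the Kapur-Olshan Index, which the Table 5 shell omits. Shell columns are thus weak evidence of the final display. This stands as a caution, but it does not close the gap, because SAP 4.4.1 does not supply the split either.

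A second reply concerns the treatment-received rule. It may be a rule for display, or it may only say how a wrongly dosed subject is classified. On the first reading the draft shell lags behind the text. On the second, a Total column does not contradict it. A reader might infer that the SAP breaches the protocol, but the documents do not settle which reading is meant, so that inference is not supported. The point rests on the safety objective, which pooled outputs leave unanswered on either reading.

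A reader might also take the title in the list of tables, "Number and percent of subjects with AE, Oral AE, TEAE, Product-related AE, Device Incidents, SAE", as proof that pooling was intended, since Table 13's title, "Bite force, AUC, and AOB summary statistics by treatment and time", names treatment. That does not follow. The titles of Tables 3, 4 and 5 do not name treatment either, yet their shells have treatment columns.

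Finally, Protocol 12.3.3 assesses safety through oral adverse events, and Listing 2 flags both oral and treatment-emergent events. Oral treatment-emergent events can therefore be picked out one by one, and the lack of a combined row in Table 14 is not a defect.

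**Conclusion.** The concern holds as a descriptive reporting gap of low severity. Produced as drafted, the safety outputs would report how many subjects had an event during the study but not on which treatment. That leaves the tolerability of each experimental adhesive undescribed.

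A reader might infer that events could never be attributed, or that the trial's conclusions are at risk. The documents support neither. The randomization schedule gives the treatment for each period under actual product names (SAP 3.1), treatment administration is recorded, and Listing 2 shows that onset dates are held. Attribution is therefore possible from the database. Nothing here touches the efficacy analysis, the validity test or the definition of study success.

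The verdict assumes that the final outputs would follow the shells. If the sponsor already intends a split by treatment, the SAP only needs to say so.

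**What to change.** Amend SAP 4.4.1 and the shells as follows.

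- **Table 14:** show it by treatment received, with four treatment columns plus Total, and count each subject once per treatment. Use the per-treatment safety numbers from Table 3 as denominators. Treatment columns need not sum to Total, because a subject may have events on more than one treatment and pre-treatment events appear only under Total. A row for oral treatment-emergent events is optional.
- **Listings 2 and 4:** add a column for the treatment received at or most recently before onset, entered as pre-treatment when onset precedes the first application.
- **Assignment rule:** state that each treatment-emergent event, including one that starts in washout, is assigned to the most recent treatment received, with no adhesive counted as a treatment.

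No testing is needed. While SAP 4.4.1 is open, correct its reference to the serious-event listing, which it calls Listing 3 while the output list and shells call it Listing 4.

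The cost is a short text change, four table columns and one listing column, all from data the trial already holds. The downside is a slightly longer table with small cell counts.
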